5.2 Sample Size

This phase III clinical trial is designed to determine a statistically significant difference in PFS by IRC between PM01183 and a control arm with PLD or topotecan in ovarian cancer patients with platinum-resistant disease.

Patients will be randomized to receive PM01183 given as 3.2 mg/m² (Arm A) or either topotecan or PLD (Arm B).

The prospective assumptions are a 30% reduction in the relative risk of progression or death (HR=0.7) to be achieved with the experimental arm (PM01183), at a one-sided 2.5% significance level with at least 90% power, following exponential distributions and fulfilling the proportional hazard assumption. Median PFS with control arm is expected to be around 3.5 months. It is forecasted that an observed HR of approximately 0.8 will have enough power to reject the null hypothesis (HR=1).

Approximately 420 patients with platinum resistant ovarian cancer will be necessary to stratify and randomize at a 1:1 ratio over 18 months (~23 patients/month). The required 332 PFS events are expected to occur around six months after randomization of the last patient. Therefore, the IDMC meeting after the IRC review to test PFS is expected to occur about one year after randomization of the last patient.

With the prospective assumptions above mentioned, about 175 PFS events are expected in the control arm and 157 in the PM01183 treatment arm.

The IDMC will review the results of the analyses. The IRC will determine the patient's best response and assign the date of objective response or progression/censoring according to the RECIST v.1.1.

5.2.1 *Futility Analysis*

A futility analysis will be performed when 210 patients are recruited (i.e., ~105 patients enrolled in each arm). The recruitment will not be put on hold.

In the futility analysis, the sponsor will make no claim of efficacy, consequently this futility analysis and the final analysis to reject the null hypothesis ($HR=1$) are planned; the significance level will be determined by the actual number of observed events by IR. To maintain scientific integrity, type II error will be controlled by a spending function defined by O'Brien-Fleming boundaries. Following the prospective assumptions, the interim analysis will occur at less than one year after start of recruitment. At this moment, with the available information collected after balancing efficacy and safety, the IDMC might recommend stopping the trial.

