All variables with a good percentage of valid cases (approximately \geq 90%) will be included in the multivariate analysis. Within the multivariate stepwise Logistic/Cox regression analysis, the chosen significance level for entering an explanatory variable into the model will be 0.05 (for all variables not in the model, the one with the smallest p-value will be entered if the p-value is less than or equal to the specified significance level). The significance level for removing an explanatory variable from the model will be 0.05 (for all variables in the model, the one with the largest p-value will be removed if the p-value exceeds the specified significance level). The parameter estimates, hazard ratios/odds ratios and p-values of the variables retained in the model will be presented.

Forest plots for PFS and OS summarizing main results, stratification and factors/covariates used in multivariate analyses will be plotted⁽²⁾.

Median follow-up (FU) time for PFS and OS will be calculated in the descriptive way, only taking into account the censored values and using the Kaplan-Meier method for reversing the censoring values as described by Parmar⁽³⁾.

Concordance between IRC and IA PFS assessments will be evaluated by means of Kaplan-Meier curves. Forest plots for response will also be performed adapting them to show relevant information (e.g. percentages will be shown instead of medians).

Sensitivity analyses for different PFS censoring will be performed. The following approaches will be calculated: 1) Date of progression based on scheduled time instead of recorded date (e.g. if progression occurs in the eleventh week and assessment would have to be done in the eighth week then the expected date is used instead of the actual date); 2) First date of progression combining IRC and IA assessments (e.g. the lowest date between IRC and IA is used); and 3) Date of progression moved to the prior tumor assessment date (e.g. if progression has not been documented in the second assessment and is documented in the third assessment then progression date is moved to the second assessment).

Proportional hazard assumption for PFS and OS will be checked by means of a Cox regression including treatment and its interaction with survival time⁽⁴⁾. In case of strong rejection of proportionality, then restricted mean survival estimates will also be calculated in addition to HR^(5,6).

Main summary of efficacy analyses

Endpoint	Population	Statistics

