11.3 Efficacy Analysis

Efficacy analysis will be carried out on the ITT population.

Table 11.3.1.1 PFS by IRC (primary analysis)

Variable	Stratification factors	p-value*
Treatment arm (main analysis)	Actual values	
Treatment arm (sensitivity)	Values reported for randomization	

*Stratified log rank test.

Progression-free survival by IRC

Table 11.3.1.2 Median FU for PFS by IRC

		Total (PM01183 and Control)
Follow-up (descriptive way)		Median (range)
Follow-up (reverse censoring method)		Median (95%CI)

Table 11.3.1.3 PFS by IRC

	PM01183	Control	Parameter	p-value
N				
Events				
Censored				
Median PFS (95% CI)			Log-Rank: HR (95% CI) :	LR: HR:
PFS at 6 months (95% CI)			Diff:	
PFS at 12 months (95% CI)			Diff:	

Kaplan Meier plot (Figure 11.3.1.3) will be shown too.

Table 11.3.1.4 Multivariate analysis of PFS by IRC (Stratification factors and treatment arm)

Analysis of maximum likelihood estimates								
Variable label	Variable values	DF	Parameter estimate	Standard error	Chi-square	Pr > ChiSq	Hazard ratio	95% Hazard ratio confidence limits

Table 11.3.1.5 Multivariate analysis of PFS by IRC

Analysis of maximum likelihood estimates								
Variable label	Variable values	DF	Parameter estimate	Standard error	Chi-square	Pr > ChiSq	Hazard ratio	95% Hazard ratio confidence limits

(see list of covariates in section 6.2).

Table 11.3.1.6 Proportional hazard assumption and restricted mean survival for PFS by IRC

Variable	PM01183	Control	Interaction p-value
Restricted mean survival [*]			

*It will be calculated if proportional hazard assumption is not met.

A forest plot (Figure 11.3.1.7) summarizing main results, stratification factors and covariates in terms of PFS by IRC will be plotted.

Progression-free survival by IA

Table 11.3.1.8 PFS by IA (Stratified log rank test)

Variable	Stratification factors	p-value*
Treatment arm (main analysis)	Actual values	
Treatment arm (sensitivity)	Values reported for randomization	

*Stratified log rank test.

Table 11.3.1.9 Median FU for PFS by IA

	Total (PM01183 and Control)
Follow-up (descriptive way)	Median (range)
Follow-up (reverse censoring method)	Median (95%CI)

Table 11.3.1.10 PFS by IA

	PM01183	Control	Parameter	p-value
N				
Events				
Censored				
Median PFS (95% CI)			Log-Rank: HR (95% CI) :	LR: HR:
PFS at 6 months (95% CI)			Diff:	
PFS at 12 months (95% CI)			Diff:	

Kaplan Meier plot (Figure 11.3.1.10) will be shown too.

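### Restricted mean survival is produced only after an undefined *strong* rejection of proportional hazards; it should be reported as a between-arm difference in every case

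*SAP*

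**What the plan says.** SAP 6.2 (Efficacy Analysis Methods) checks proportional hazards for PFS and OS by a Cox regression containing treatment and its interaction with survival time. It gives no significance level and no transformation of time. The consequence of the check is: "In case of strong rejection of proportionality, then restricted mean survival estimates will also be calculated in addition to HR".

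The shells in SAP 11.3 that carry this result are Table 11.3.1.6 (PFS by IRC), Table 11.3.1.13 (PFS by IA) and Table 11.3.1.27 (OS). Their columns are PM01183, Control and an interaction p-value. The footnote on the restricted mean survival row reads: "It will be calculated if proportional hazard assumption is not met".

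Other outputs do not depend on the check. The stratified log-rank test on the ITT population is the primary analysis (SAP 6.2 and Table 11.3.1.1). Tables 11.3.1.3, 11.3.1.10 and 11.3.1.24 always give the HR with 95% CI, medians, landmark estimates with between-arm differences, and a Kaplan-Meier plot.

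The design itself assumes proportionality. SAP 5.2 sets the trial up "at a one-sided 2.5% significance level with at least 90% power, following exponential distributions and fulfilling the proportional hazard assumption".

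**The concern.** When the hazard ratio changes over time, a single Cox HR is an average whose weights depend on the censoring pattern. Restricted mean survival is the one numerical whole-curve summary in the SAP that does not need proportional hazards. It is withheld unless a test rejects, and failure to reject such a test is weak evidence of proportionality. If the test has low power, the summary will often be missing in the trials where it would help most.

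The rule is also incomplete in four ways that can be read from the text alone:

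1. *Strong* has no cut-off, although the same section gives 0.05 for stepwise entry and removal.
2. The text and the shell footnotes set different triggers.
3. No truncation time is given, so it would be chosen after the data are seen.
4. The shells show one value per arm, with no difference and no interval.

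The question is not academic for OS. SAP 6.1 qualifies its OS power statement for the impact of later therapies, and SAP 8.5 plans special attention to subsequent platinum. Either could make the OS hazard ratio vary with time.

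**Working it through.** **Inputs from SAP 5.2 and 6.1.** 420 patients randomized 1:1 over 18 months; HR 0.70; one-sided 2.5%; at least 90% power; control median PFS 3.5 months, exponential; 332 PFS events; scans every eight weeks.

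**Reproducing the plan's figures.**
- Events (Schoenfeld, 1:1): 4 × (1.960 + 1.282)² / (ln 0.70)² = 4 × 10.51 / 0.1272 ≈ 331, against 332 stated.
- Power at 332 events: Φ(0.3567 × √332 / 2 − 1.960) = Φ(1.289) = 90.1%.
- Largest significant HR: exp(−2 × 1.960 / √332) = 0.806, matching the stated value of about 0.8.
- Exponential accrual without dropout gives about 175 control and 157 PM01183 events near month 20.6. This matches the SAP's split: "about 175 PFS events are expected in the control arm and 157 in the PM01183 treatment arm".

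The design figures therefore hold, under proportional hazards.

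**Simulating the check.** Each trial has the inputs above and is cut at event 332. Arm A has a piecewise-constant HR against the control hazard ln 2 / 3.5. A Cox model with treatment and treatment × time is fitted, and the interaction is tested by a two-sided Wald test. There is no dropout and no stratification. The hazard shapes and the two significance levels are assumptions, because the documents give neither. A miss means that the test does not reject, so restricted mean survival would not be produced.

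*Set A: progression recorded at 8-week scans, 1,500 trials per row*

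| HR over time | Missed at 5% | Missed at 1% |
|---|---|---|
| 1.0 for 2 months, then 0.50 | 44% | 67% |
| 0.50 for 3.7 months, then 1.0 | 32% | 57% |
| 0.50 for 2 months, then 0.90 | 67% | 87% |
| 0.55 for 3.7 months, then 1.2 (crossing) | 20% | 43% |
| 1.2 for 2 months, then 0.50 (crossing) | 23% | 43% |

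*Set B: continuous event times, 4,000 trials per row (100% minus the rejection rate)*

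| HR over time | Missed at 5% | Missed at 1% |
|---|---|---|
| 1.0 for 2 months, then 0.6 | 64% | 83% |
| 1.0 for 2 months, then 0.5 | 43% | 67% |
| 1.0 for 4 months, then 0.5 | 34% | 58% |
| 0.5 for 4 months, then 1.0 | 32% | 57% |
| 0.6 for 4 months, then 1.0 | 56% | 79% |
| 0.6 for 6 months, then 1.2 (late reversal) | 40% | 63% |
| 1.3 for 2 months, then 0.6 (crossing) | 29% | 53% |
| 1.3 for 4 months, then 0.5 (crossing) | 13% | 31% |
| 0.6 for 4 months, then 1.3 (crossing) | 21% | 43% |
| 0.5 between 2 and 6 months only | 95% | 99% |

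Under a true constant HR of 0.70 the test rejects in about 5% of trials at the 5% level. It is correctly sized, and the limitation is power. In the second row of Set A the mean reported HR is 0.71, so the HR alone would look like a true constant 0.70. At 1%, restricted mean survival is omitted more than half the time in 8 of the 10 Set B shapes.

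Using log time instead of linear time, or scan times instead of continuous times, moves individual figures by up to about 25 points in either direction without changing the picture.

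**The two triggers side by side.** With an interaction p-value of 0.03, the SAP 6.2 text could be read as not strong, so no estimate. The footnote could be read as assumption not met, so estimate. Both readings are open because neither place gives a number.

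**OS.** Not simulated. The documents give no OS event number and no control OS median as design assumptions.

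**The case against.** The strongest case against is that little depends on this gate. The primary stratified log-rank test ignores it, so the primary type I error is untouched. The HR never stands alone: curves, medians and landmark differences always accompany it, and none of these needs proportional hazards. The miss rates rest on assumed shapes and an assumed meaning of *strong*. At 5%, four of the five Set A shapes are detected more often than missed, and the plainer footnote trigger might well be read as 5%. Linear time is only the literal reading of the SAP. All of this stands, and it limits the point to a supportive analysis.

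A reader might infer three stronger things that the documents do not support:

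- **That the SAP concludes proportionality from a non-significant test.** It says only that the assumption will be checked, and the shells print the interaction p-value.
- **That the reported effect measure is switched according to the data.** The HR is reported in every case, and restricted mean survival is an addition to it.
- **That no treatment contrast is planned on the restricted mean scale.** The shells lack one, but SAP 6.2 cites for the method a paper whose title concerns estimating the treatment effect by restricted mean survival time. The gap is in the specification and is not proof of intent.

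What the objection does not remove is the undefined and conflicting trigger, the missing truncation time, and the limited power of the gate.

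**Conclusion.** The point holds as a low-cost improvement to a supportive analysis. SAP 6.2 and the shells make restricted mean survival conditional on one interaction test, with no cut-off, two different triggers, no truncation time and no between-arm estimate in the shells.

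For PFS at 332 events, moderate delayed or waning effects go undetected in about 30–70% of trials at 5% and 55–88% at 1%. For the moderate crossing shapes the figures are about 20–25% and 41–46%; the three Set B shapes labelled crossing span 13–29% and 31–53%. These sizes depend on the assumed shapes and levels, on linear time and on no dropout, and they do not extend to OS. The four drafting gaps depend on none of these assumptions.

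The validity of the primary test is not in question. Only the presence of a supplementary whole-curve estimate depends on the data.

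**What to change.** In SAP 6.2 and Tables 11.3.1.6, 11.3.1.13 and 11.3.1.27:

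- Report the restricted mean survival difference (PM01183 minus control) with 95% CI for PFS by IRC, PFS by IA and OS in all cases.
- Fix the truncation times now, for example 12 months for PFS and 24 months for OS, which are landmarks the plan already uses. Both should be estimable: 332 PFS events arrive near month 20.6 under the design assumptions, and the SAP places the final OS analysis 24 months after the last randomization.
- Keep the treatment-by-time test as a description, and state its time function.
- Delete the conditional wording in SAP 6.2 and in the three footnotes, which also removes the conflict between them.

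If the sponsor prefers to keep a condition, the minimum is one stated significance level used in both places, a stated time function, a fixed truncation time, and a difference with its interval in the shells.

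The cost is a few lines of SAP text and one row in each of three tables. The method and its references are already in the SAP, and the primary test, alpha and sample size do not change. The small downside is one more supportive effect measure to report.

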6.2 Efficacy Analysis Methods

Time-to-event variables (PFS, OS and DR) and their set time estimates (i.e., PFS 6/12 and OS 12/24) will be analyzed according to the Kaplan-Meier method.

The stratified log-rank test, using actual values for all randomization strata variables, on the ITT population will be primarily used to compare the time-to-event variables. If the actual value is not a pre-defined category the value will be added to the most similar category (e.g., patients with more than three prior chemotherapy lines will be included in the 3-lines category).

Unstratified log-rank tests will also be calculated as supportive analyses.

The symmetry of tumor evaluations between the different arms will be examined. Wilcoxon test to compare time to disease assessments between treatment arms will be used to assess symmetry of evaluations. Moreover, Kaplan-Meier curves of the time from randomization and first and second disease assessment will be plotted. If necessary, internal symmetry between the two different treatments in the control arm will be checked following the same approach.

Cox regression will be used to calculate the risk reduction (PFS, OS and DR) and to evaluate the influence of the stratification variables and other potential prognostic factors on the time-to-event efficacy endpoints.

Counts and percentages, with their corresponding exact 95% confidence intervals, will be calculated for the binomial endpoints (i.e., response rate). The Fisher's exact test (univariate analyses) and logistic regressions will be used to compare the response rates.

Waterfall plots will be used to describe the best variation of the sum of target lesions diameters during the treatment.

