Multivariate models (main effects or including interaction terms, if appropriate) will include all stratification factors and/or prognostic factors/covariates widely reported and recognized by the scientific community: treatment (PM01183 vs. control), ECOG PS (0 vs. ≥ 1 or coded as 0 vs. 1 vs. 2) prior platinum-free interval (1-3 months vs. >3 months or used as continuous variable), prior chemotherapy (1-2 vs. 3 lines or coded as 1 vs. 2 vs. 3), geographical area (USA vs. Europe vs. rest of the world), investigator's preference for the control arm (Topotecan vs. PLD), age, age at diagnosis, race (caucasian vs. other), histology type (serous/papillary vs. other), histology grade (poorly/undifferentiated vs. other), primary tumor site (ovarian vs. other), FIGO stage at diagnosis (metastatic/locally advanced [stage III] vs. other), FIGO stage at study entry (metastatic vs. locally advanced [stage III]/other), BRCA status (mutated vs. other), clinical/radiological signs of intestinal subocclusion at entry (yes vs. no), site of current disease: lung/liver (yes vs. no), liver metastases (yes vs. no), number of prior metastatic sites (≤ 2 vs. >2), body mass index (BMI), height, weight, body surface area (BSA), time from diagnosis to first infusion, prior cytoreduction (optimal vs. suboptimal vs. no surgery), prior radiotherapy (yes vs. no), platinum resistance (primary vs. secondary), clinically evidence of ascites at baseline (yes vs. no), time elapsed from last dose of last prior platinum-containing regimen to randomization, prior antiangiogenic treatment

with bevacizumab (yes vs. no), prior PARPi (yes vs. no), presence of any bulky (< 50 mm vs. \geq 50 mm) lesion at baseline, measurable disease (yes vs. no), sum of all target lesion diameters, baseline CA-125, albumin value at baseline, PFS prior line, response to last platinum therapy (yes vs. no) and baseline global QoL. In addition, continuous variables categorized as discrete variables will also be investigated in the continuum range and if the adjustment is better then the continuous variable will be selected in the model.

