PFS by IRC (primary endpoint)	ITT population	-Stratified log rank test
OS	ITT population	-Stratified log rank test -Unstratified log rank test -Kaplan Meier estimates -Univariate Cox regression -Multivariate Cox regression
PFS by IRC/IA	ITT population	-Stratified log rank test (IA) -Unstratified log rank test -Kaplan Meier estimates -Univariate Cox regression -Multivariate Cox regression

Endpoint	Population	Statistics
Response rate by IRC/IA	ITT population	-Fisher exact test -Logistic regression
Duration of response by IRC/IA	ITT population (in patients achieving a response)	-Unstratified log rank test -Kaplan Meier estimates

ITT: Intention-to-treat; IRC: Independent Review Committee; IA: Investigator Assessment; PFS: Progression Free Survival; OS: Overall Survival

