PFS at 12 months (95% CI)			Diff:	

Kaplan Meier plot (Figure 11.3.1.19) will be shown too.

- Date of progression moved to the prior tumor assessment.

Table 11.3.1.20 PFS moved to the prior tumor assessment by IRC

	PM01183	Control	Parameter	p-value
N				
Events				
Censored				
Median PFS (95% CI)			Log-Rank: HR (95% CI) :	LR: HR:
PFS at 6 months (95% CI)			Diff:	
PFS at 12 months (95% CI)			Diff:	

Kaplan Meier plot (Figure 11.3.1.20) will be shown too.

Table 11.3.1.21 PFS moved to the prior tumor assessment by IA

	PM01183	Control	Parameter	p-value
N				
Events				
Censored				
Median PFS (95% CI)			Log-Rank: HR (95% CI) :	LR: HR:
PFS at 6 months (95% CI)			Diff:	
PFS at 12 months (95% CI)			Diff:	

Kaplan Meier plot (Figure 11.3.1.21) will be shown too.

Overall survival

Table 11.3.1.22 OS (Stratified log rank test)

Variable	Stratification factors	p-value*
Treatment arm (main analysis)	Actual values	
Treatment arm (sensitivity)	Values reported for randomization	

*Stratified log rank test.

Table 11.3.1.23 Median FU for OS

	Total (PM01183 and Control)	
Follow-up (descriptive way)	Median (range)	
Follow-up (reverse censoring method)	Median (95%CI)	

Table 11.3.1.24 OS

	PM01183	Control	Parameter	p-value
N				
Events				
Censored				
Median OS (95% CI)			Log-Rank: HR (95% CI) :	LR: HR:
OS at 12 months (95% CI)			Diff:	
OS at 24 months (95% CI)			Diff:	

Kaplan Meier plot (Figure 11.3.1.24) will be shown too.

Table 11.3.1.25 Multivariate analysis of OS (Stratification factors and treatment arm)

Analysis of Maximum Likelihood Estimates								
Variable label	Variable values	DF	Parameter estimate	Standard error	Chi-square	Pr > ChiSq	Hazard ratio	95% Hazard ratio confidence limits

Table 11.3.1.26 Multivariate analysis of OS

Analysis of Maximum Likelihood Estimates								
Variable label	Variable values	DF	Parameter estimate	Standard error	Chi-square	Pr > ChiSq	Hazard ratio	95% Hazard ratio confidence limits

(see list of covariates in section 6.2).

Table 11.3.1.27 Proportional hazard assumption and restricted mean survival for OS

Variable	PM01183	Control	Interaction p-value
Restricted mean survival*			

*It will be calculated if proportional hazard assumption is not met.

A forest plot (Figure 11.3.1.28) summarizing main results, stratification factors and covariates in terms of OS will be plotted.

Objective response and duration of response by IRC

Table 11.3.1.29 Response rate by IRC

Response	PM01183		Control		p-value
	N	%	N	%	
CR					

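### No hazard ratio and CI is designated to go with the stratified primary PFS test, and the stepwise models would show the treatment effect only when it is significant

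*SAP*

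**What the plan says.** SAP section 6.2 makes the log-rank test stratified by the actual values of the three randomization factors, on the ITT population, the main comparison for time-to-event endpoints. In the summary table that closes 6.2, the row for the primary endpoint lists that test and nothing else. Its shell in section 11.3, "Table 11.3.1.1 PFS by IRC (primary analysis"), has one result column, the p-value, for the main analysis and for a sensitivity row using the strata reported at randomization. Tables 11.3.1.8 (PFS by IA) and 11.3.1.22 (OS) have the same layout.

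Effect estimates are covered by a general sentence: "Cox regression will be used to calculate the risk reduction (PFS, OS and DR"). The summary row for PFS by IRC/IA lists "Stratified log rank test (IA) -Unstratified log rank test -Kaplan Meier estimates -Univariate Cox regression -Multivariate Cox regression", and the OS row likewise names only univariate and multivariate Cox. Neither the SAP nor the protocol names a stratified Cox model.

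Two displays always give an HR with CI for PFS by IRC. "Table 11.3.1.3 PFS by IRC" puts an HR beside a log-rank result without naming the model. "Table 11.3.1.4 Multivariate analysis of PFS by IRC (Stratification factors and treatment arm") gives the treatment HR with the stratification factors as covariates. The OS counterpart of the second is "Table 11.3.1.25 Multivariate analysis of OS (Stratification factors and treatment arm").

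For the long-covariate models, the 6.2 list begins with "treatment (PM01183 vs. control"). Entry is at 0.05, and for exit "The significance level for removing an explanatory variable from the model will be 0.05". No variable is exempted, and only retained variables are presented.

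**The concern.** There are two gaps.

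First, readers will put an HR next to the primary p-value, and the plan does not say which one. The SAP itself describes success in HR terms, with an observed HR of about 0.8 expected to reject the null, but does not say from which model. If the HR shown is unstratified, it is not the estimate that the stratified test corresponds to. When the strata are prognostic it is pulled toward 1, because the HR is non-collapsible. Its CI can then include 1 although the primary test succeeded. Leaving the choice open also means that the headline estimate could be picked after the data are seen.

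Second, a treatment HR that is printed only when p is at most 0.05 is a selected estimate. It is absent when the effect is small and exaggerated when it appears.

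**Working it through.** **Inputs from SAP 5.2:** 420 patients, 1:1, 18 months' accrual, control median 3.5 months, exponential, HR 0.70, one-sided 2.5%, at least 90% power, 332 events. **Assumed, because the documents give no values:** prevalences of 50/40/30% for the three factors, and factor HRs between 1.0 and 2.0.

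**1. The plan's own figures reproduce.**
- Events: 4(1.960 + 1.282)² / (ln 0.70)² = 330.4, so 331 (Schoenfeld), against 332 stated.
- Power at 332 events: 90.1%.
- Critical HR: exp(−1.96 × 2/√332) = 0.806, matching the SAP's approximate 0.8.
- Split by arm at 332 events under the exponential model: 175.8 and 156.2, against 175 and 157 stated.
- Approximate 95% CI, HR × exp(±1.96 × 2/√332): 0.565 to 0.868 at HR 0.70, and 0.645 to 0.992 at HR 0.80. The second shows how little room there is near the boundary.

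**2. Which HR matches the test.** The stratified log-rank test is the score test from a Cox model with the same strata, so that model's CI should agree with the test almost always. This was checked with 2,000 simulated trials per scenario: 1:1 within the 8 strata, uniform accrual, cutoff at event 332, no dropout.

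| Factor HRs | Mean unstratified HR, true 0.70 | Test significant but unstratified CI includes 1, true 0.70 | Same, true 0.80 |
|---|---|---|---|
| 1/1/1 | 0.697 | 1.0% | 2.6% |
| 1.3/1.3/1.3 | 0.710 | 2.5% | 4.0% |
| 1.5/1.4/1.3 | 0.712 | 2.3% | 4.6% |
| 2.0/1.6/1.4 | 0.728 | 6.0% | 10.5% |
| 2/2/2 | 0.740 | 8.8% | 14.6% |

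At true HR 0.70 the stratified Cox mean stays at 0.697 to 0.703, and the model with the factors as covariates (the Table 11.3.1.4 type) at 0.696 to 0.702. The same kind of discordance is 0.0–0.2% for stratified Cox and 0.6–1.3% for the covariate model at HR 0.70. At HR 0.80 it is 0.1–0.3% and 1.5–2.6%. The reverse case, a non-significant test with an unstratified CI that excludes 1, occurs in 0.8–1.8% (HR 0.70) and 1.9–4.3% (HR 0.80).

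A second simulation, with 1,200 trials per scenario, each factor at 50% and a common factor HR of 1.0 to 2.0, gave 1.1–9.8% at HR 0.70 and 2.0–14.7% at HR 0.80 for the unstratified CI. The stratified Cox CI disagreed with the test, in either direction, in at most 0.4%.

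**3. Stepwise rule.** With SE = 2/√332 = 0.1098, treatment is not retained with probability P(|Z| < 1.96), where Z has mean ln(HR)/0.1098. If it is retained, the observed HR is below about 0.806. The simulated models held treatment, the three stratification factors, three prognostic covariates and eight null covariates.

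| True HR | Not retained, formula | Not retained, stepwise simulated (runs) | Median HR if retained, formula | Median HR if retained, simulated |
|---|---|---|---|---|
| 0.70 | 9.9% | 10.8% (390) | 0.691 | 0.693 |
| 0.75 | 25.4% | 30.8% (425) | 0.724 | 0.710 |
| 0.80 | 47.1% | 44.8% (397) | 0.747 | 0.740 |

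A repeat simulation gave about 6%, 31% and 45% not retained. At HR 0.75 the first simulation exceeds the formula by (0.308 − 0.254)/√(0.254 × 0.746/425) ≈ 2.6 Monte Carlo standard errors, so these rates should be read as approximate. The event count applies to PFS; OS will have a different number.

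**4. Does the wording force treatment in?** Section 6.2 says that the multivariate models will include the listed factors. It also says that all variables with about 90% valid cases will be included in the multivariate analysis, and then applies entry and removal to them. In that second place, inclusion means being a candidate. Nothing exempts treatment.

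**The case against.** The plan does not lack an HR for PFS. Tables 11.3.1.3 and 11.3.1.4 both prespecify one with its CI, and 11.3.1.4 shows the factor-adjusted treatment effect whatever its significance. In the simulations that model gives essentially the same mean HR as stratified Cox, with discordance about one percentage point higher at the design effect. That the HR in 11.3.1.3 is unstratified is an inference from the model list, and 6.2 already calls the unstratified log-rank test supportive. The largest discordance figures need all three factors to have HR 2.0; at 1.3 to 1.5 they are 2.3–2.5% at HR 0.70. About 1% occurs even with no prognostic effect, so not all of it is attenuation. The attenuation is also conservative and small beside the CI width. The stepwise models are secondary.

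All of this stands as a limit on size. It does not answer the point. Neither HR is designated, so the estimate that accompanies the primary test remains open. A factor-adjusted Cox model would also be a defensible choice if named, but the stratified model matches the test more closely at the same cost. That treatment effects appear elsewhere does not make the stepwise estimate unselected.

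**Conclusion.** The concern holds as a gap in estimation and reporting. The primary test has no designated HR and CI. If the unstratified HR is the one quoted, then at true HR 0.70 it averages up to 0.74, and its CI contradicts a significant primary test in roughly 1 to 9% of trials (up to about 15% at true HR 0.80). The upper ends rest on strong assumed factor effects; moderate ones give 2 to 5%. Under the stepwise rule as written, treatment would be missing from about 10%, a quarter to three tenths, and 45 to 47% of PFS models at HR 0.70, 0.75 and 0.80. When it is retained at a true HR of 0.80, the median reported HR is about 0.74 to 0.75. Type I error, power, the 332 events and the primary decision rule are untouched. The change should be made, but the validity of the primary test does not depend on it.

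**What to change.** - State in SAP 6.2 that the effect estimate for PFS and OS is the HR with 95% CI from a Cox model stratified by the same three factors, at actual values, as the log-rank test. Add it to Tables 11.3.1.1, 11.3.1.8 and 11.3.1.22.
- Label the HR in Tables 11.3.1.3, 11.3.1.10 and 11.3.1.24 as unstratified and supportive.
- In the stepwise Cox models (Tables 11.3.1.5, .12 and .26) and logistic models (Tables 11.3.1.31 and .37), force in treatment and the three stratification factors. Apply the 0.05 rule to the other covariates only, and always report the treatment estimate with its CI.

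The cost is a few sentences, a STRATA statement, an INCLUDE option and one extra column in three shells. It needs no new data and no change to the primary test.
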